5.2.1 Research Participants Protections Against Risks

The expected risks associated with this research have been deemed minimal by the Minneapolis VA IRB. All potential participants will be actively engaged in healthcare; they will have been identified through the electronic record in which they have had at least two visits with a provider in the past year. Also, as part of standard VA policy, Veteran patients complete annual suicidality screening. The project team has developed

plans for risk mitigation that meet or exceed what currently exists within the VA health system. See Table 1 for plans to protect participants against risks and Sections 5 and 6 for monitoring and reporting plans.

As part of the study, we will monitor safety after consent has been secured (e.g. screening, intervention, follow up). Safety concerns may be learned of actively (e.g. through querying at screening or in surveys) or passively (e.g. participant discloses during any communication at any point on Webex, by email or on phone).

All participant facing staff will be trained, certified and monitored by investigators to ensure the satisfactory implementation of safety and monitoring procedures. In the event a staff member learns a participant is at risk of experiencing a serious adverse event (e.g., suicidality) they will implement safety procedures developed by our team's clinical health experts (summarized in Table 1 and detailed in the manual of operations).

MPIs and Co-Investigators will conduct, at least monthly, a review of safety data and meet with project staff to discuss any problems or concerns that arise; additional training to implement risk monitoring, documentation and implementation of safety procedures will occur as necessary.

Table 1. Protection Against Risks

Type of Risk	Risk Mitigation
Confidentiality and Data Safety	
• All staff receive HIPAA and data safety training that includes maintaining the confidentiality and security of research records and information.• Details regarding the protection of study databases and source documentation is provided in sections 8.
Health Surveys (All)	
• All participants will have the option of skipping any interview or questionnaire questions they do not wish to answer.• All surveys will be prefaced by the following*: "Our first priority is your safety. The following questions relate to your emotional and mental wellbeing. We recognize that sharing this information can be challenging. Please remember while answering these questions to take care of yourself and if you are feeling upset and

	
would like help, please call the Veterans Crisis line by dialing 988 and pressing 1.”
 
• All surveys will have the following message at the end*: “Our first priority is your safety. The previous questions relate to your emotional and mental wellbeing. We recognize that sharing this information can be challenging. Please remember to take care of yourself, and if you are feeling upset and would like help, please call the Veterans Crisis Line by dialing 988 and pressing 1. 
*Language based on suggestions by our Veteran Advisors

Health Surveys (Follow Up Only)	
• All participants will be queried for Serious Adverse Events. “Since your last survey, have you experienced a NEW or WORSENING medical issue or event which resulted in any of the following:
a. Overnight stay in a hospital?” (no, yes with open fields to describe when it occurred, what happened, if still being treated)b. Problem that results in a severe or permanent disability?” (no, yes with open fields to describe when it occurred, what happened, if still being treated)c. A life-threatening injury or event? (no, yes with open fields to describe when it occurred, what happened, if still being treated)
Screening procedures	
• Potential research participants will undergo baseline screening to ensure they meet eligibility criteria and it is safe for them to participate.• Baseline screening will be conducted by staff applying structured checklists to existing electronic medical records review• Screening staff will be trained and supervised by the clinical psychologist MPI and Co-Is responsible for data collection. The following is considered exclusionary:
• Hospitalization for a severe mental illness-related issue in the past 6 months; active psychotic symptoms, suicidal ideation, or manic episodes; active substance use disorder that is poorly controlled.• Staff will be trained to actively monitor for potential emotional distress during baseline eligibility calls and to implement safety procedures if needed. The manual of operations details steps for assessing the nature of the situation, responding appropriately to ensure participant safety, documenting the event and notifying the Project Director and the MPIs (see Section 6). Participants in which imminent risk for suicidality is possible will be offered a warm handoff to the Veterans Crisis Line; if they decline, or disconnect, staff will immediately 1) contact the local police department to conduct a wellness check, then 2) contact the Veterans Crisis line to report event and 3) contact the participants' local suicide prevention team.

Intervention	
• The RAMP intervention has been designed to include activities and exercises that are suitable for a range of abilities and preferences. The mind-body skill practices are short in duration (~5-10 minutes), lowering the risk of emotional discomfort or psychological events.• Participants will also be given the option to refrain from participating in activities that feel uncomfortable.• Facilitators will be trained and supervised by the clinical psychologist MPI, chiropractic MPI, and Co-Is with clinical pain management experience to actively monitor for potential emotional or physical distress during session activities and how to implement safety procedures. The manual of operations details steps for assessing the nature of the situation, responding appropriately to ensure participant safety, documenting the event and notifying the Project Director and the MPIs (see Section 6).• Participants in which imminent risk for suicidality is possible will be offered a warm hand off to the Veterans Crisis Line; if they decline, or disconnect, staff will immediately 1) contact the local police department to conduct a wellness check, then 2) contact the Veterans Crisis line to report event and 3) contact the participants' local suicide prevention team.
---------------------	----------------------------------------------------------------------------------------------------------------------------------------------------------------------------------------------------------------------------------------------------------------------------------------------------------------------------------------------------------------------------------------------------------------------------------------------------------------------------------------------------------------------------------------------------------------------------------------------------------------------------------------------------------------------------------------------------------------------------------------------------------------------------------------------------------------------------------------------------------------------------------------------------------------------------------------------------------------------------------------------------------------------------------------------------------------------------------------------------------------------------------------------------------------------------------------------------------------------------------------------------------------------------------------------------------------------------------------------------------------------------------------

6 Adverse Event/ Unanticipated Problems

All project team members will undergo project-specific human subjects training that addresses risks to subjects; protection against risks; potential benefits of research to subjects and others; and the importance of knowledge to be gained. Additionally, all study personnel will be required to complete training in the Responsible Conduct of Research every three years. This includes online CITI training in responsible conduct of research, good clinical practice, and human research protections. Current human subjects training records are regularly updated by the Minneapolis VA IRB and checked annually at Continuing Review.

All project team members will be trained in study specific protocols relevant to their role, including detailed safety procedures to mitigate risk to participants (see Section 5 and Table 1 above). We will use active and passive monitoring of adverse events and unanticipated problems in the study. Serious or possibly related adverse events and unanticipated problems can be learned about in the following ways:

- From participants, who will be encouraged to contact the Project Director or an MPI
- From direct queries in the self-report surveys
- From observations by project staff during baseline screening calls, interventions, and other interactions with participants

Participants who experience possibly related serious adverse events and unanticipated problems will be contacted by the Project Director or delegate to gather information for adverse event reporting (see Section 6.1 below) and ensure safety procedures are followed (see Section 5 above).

Events identified as serious adverse events or unanticipated problems will be adjudicated by the MPIs and Co-Is for: confirmation of severity, relatedness and expectedness based on the definitions below.

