Our power calculation uses the Brief Pain Inventory (BPI) interference scores over the entire follow-up period as the primary outcome measure. The primary outcome uses a repeated measures approach that takes into account assessments at 3 and 6 months with a single test of significance. Secondary outcomes will evaluate the time points separately. For our primary analysis we estimate up to 20% attrition, so at least 500 people will need to be randomized to obtain a sample of 400 people with complete data. 200 participants in each arm will yield 90% power, with an alpha of 0.05, to reject the null hypothesis of equal means over the repeated follow-up time points (i.e., 3 and 6 months) if the arms differ by an effect size of 0.3 or greater. This includes a conservative estimate that the repeated outcome measures are highly correlated ($r=0.7$) and even with only 1 time point there is power to detect effect sizes of 0.32. Analyses that are stratified by subgroups as small as 70 people per arm (i.e., equivalent to restricting to only women or minority Veterans) would have approximately 90% power to detect differences of 0.50. However, these would only be exploratory in nature and not adjusted for multiple comparisons. While our goal is to achieve 500 randomized participants, our intervention will roll out in large waves so precisely hitting a randomized sample number is difficult. Therefore, we asked for an administrative IRB approval to exceed this goal and enroll up to 550 participants.

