We will use an intention-to-treat approach. Preliminary descriptive analyses will summarize the distributions of the baseline measures across treatment arms overall and will similarly assess the outcome distributions across assessment time points (i.e., baseline, 3, and 6 months). We will summarize the completeness of the self-reported outcome assessments and examine associations between completeness and baseline measures as well as the association with secondary outcome assessments that are collected from the electronic medical record (e.g., medications, health care utilization related to pain treatment). Initial analyses will use all available follow-up data and subsequent sensitivity analyses will examine the potential effect of response bias. For analyses of the primary outcome, all repeated measurements of the BPI interference score will be fitted in a mixed model for repeated measures as a function of the group assignment, while controlling for time points and baseline values of the outcome as fixed effects, with participants as random effects. Between-group differences over the entire follow-up period (average of 3 and 6 months) will be the primary test of treatment group differences. Between-group differences will be estimated for each of the individual time points as secondary outcomes. Similar to the methods described above for the primary analyses, weighted selection model analyses will examine the sensitivity of the initial results to response biases. To do this, we will fit a series of weighted selection model analyses. Each analysis will use an expectation-maximization algorithm to estimate weights to assign to potential values of the missing outcomes for use in the regression model. The secondary outcomes will be similarly analyzed

using the same linear mixed effect models for normal continuous measures and appropriate generalized linear mixed effect models for non-normal measures.

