6.2 Time Period and Frequency for Event Assessment and Follow-Up

The Project Director or designee will record all adverse events or UPIRTSOs the project team is made aware of occurring any time after consent until 30 days after the last day of study participation. Study related SAEs will be followed to stabilization/resolution.

Characteristics of an Adverse Event

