customized research tracking application, while the VINCI platform provides a robust environment for pooling the primary research collected data with direct connections to daily or weekly updated mirrors of nearly the entire VHA EHR. VINCI also provides access to extensive storage area networks, drives, file shares, databases, SharePoint for collaboration and correspondence sites, SAS/Grid, and servers containing virtual machines with an extensive collection of software called the VINCI Workspace. We requested and were provided access to the Joint Legacy Viewer (JLV) in order to capture the highest follow-up response rate that is feasible. It is very important that we reach the participants in a timely manner; being able to access current address and phone numbers will help in tracking hard to reach participants. A secure link between local VA secure servers Qualtrics FedRAMP will be created. Limited study specific data will be collected on Qualtrics FedRAMP and will contain a study specific participant ID code. VINCI allows individual researchers and their staff the means to securely conduct their research projects within a secure and well controlled technical environment. All of these VA systems undergo backups of the servers nightly and servers are updated when new security patches become available.

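### After enrolment, deaths and SAEs are found only through surveys, self-report and staff contact, with no scheduled EHR or vital-status check, and RAMP is watched more closely than Usual Care

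*Combined protocol and SAP*

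**What the plan says.** **Detection.** DSMP section 6 names three sources for serious events: participants, who are encouraged to contact the team; "From direct queries in the self-report surveys"; and what staff notice in screening calls, sessions and other interactions. The explicit SAE questions (overnight hospital stay, severe or permanent disability, life-threatening event) are listed for follow-up surveys only (DSMP 5.2.1, Table 1). DSMP 6.2 has staff record events that come to the team's notice "until 30 days after the last day of study participation". Death from any cause heads the criteria for a serious event in DSMP 6.2.1.

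**Contact by arm.** The Schedule of Activities (section 2.3) marks adverse events at intervention sessions as well as at 3 and 6 months, and section 3.3.3 has participants monitored in all sessions. Usual Care participants only complete follow-up surveys (section 5.1.2). The DSMB's closed report shows SAEs by group (DSMP 7.5).

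**Record linkage.** DSMP 8.2 describes a platform with "direct connections to daily or weekly updated mirrors of nearly the entire VHA EHR". Section 5.8 refers to secondary outcomes "collected from the electronic medical record (e.g., medications, health care utilization related to pain treatment". The EHR also serves recruitment and the chart review for exclusions, and the Joint Legacy Viewer supplies contact details.

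**Attrition.** Section 5.8 states: "For our primary analysis we estimate up to 20% attrition".

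**The concern.** A person who has died cannot answer a survey, and a person in hospital is less likely to. If finding an event depends on contact, missing safety data are informative, and the events most likely to be missed are the most serious. Relatedness is adjudicated only for events already identified, and the reporting deadlines for deaths and unanticipated SAEs run from the time the team learns of them. An event nobody hears about is therefore neither adjudicated nor reported.

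The arms also differ in how hard events are looked for. With equal true risk, closer observation alone would show more events under RAMP, while unequal non-response could push the comparison either way. The DSMB could not tell these apart from the by-group tables. The data needed to avoid the problem are largely linked to the study already.

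**Working it through.** **1. What each route needs.** Self-report needs a participant able to make contact. The survey query needs a returned survey. Staff observation needs an interaction. None works for a participant who has died or fallen silent unless someone else tells the team.

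**2. Scheduled occasions by arm.** RAMP has 9 sessions (section 5.1.2) and 2 surveys, so 9 + 2 = 11 occasions. A participant at the adherence threshold of 6 of 9 sessions who returns both surveys has 6 + 2 = 8. Usual Care has 2. After the sessions end, both arms have surveys only. After the 6-month survey neither has a safety query; the end-of-participation contact in DSMP 9.1 is a notification.

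**3. Where the 20% comes from.** The plan's figure is 400 complete cases: 400 / (1 − 0.20) = 500 randomised, as stated. The power claim also reproduces. Inputs from section 5.8 are 200 per arm, effect 0.3, correlation 0.7 and alpha 0.05 (two-sided assumed). The SD of the mean of two scores is √((1 + 0.7)/2) = 0.922. Power is Φ(0.3 / (0.922 × √(2/200)) − 1.96) = 90.2%, against 90% stated. The 20% is thus a planning bound on incomplete primary-outcome data. It is not a rate of answering no survey.

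**4. Size of the group.**
- At 20%: 500 × 0.20 = 100, about 50 per arm if loss is equal.
- At the earlier trial's 86% follow-up at 12 months (section 5.2.2): 500 × 0.14 = 70, about 35 per arm.
- At the approved ceiling of 550: 550 × 0.20 = 110 and 550 × 0.14 = 77.

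**5. Worst-case share of SAEs captured.** Let d be the non-response proportion and k the SAE risk in non-responders relative to responders. Assume no event in a non-responder is found by any route. The share is (1 − d) / ((1 − d) + d·k).

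| d | k = 1 | k = 2 | k = 3 |
|---|---|---|---|
| 0.20 | 80% | 67% | 57% |
| 0.14 | 86% | 75% | 67% |

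The documents give no k. These are floors, because sessions, late surveys and tracing calls will find some events.

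**6. Events in absolute terms, by assumption.** The documents give no event rates. With 100 non-responders at the same risk as everyone else, an assumed 6-month mortality of 0.5% to 2% gives 0.5 to 2 deaths among them. The probability of at least one is 1 − 0.995^100 = 0.39 to 1 − 0.98^100 = 0.87. An assumed 6-month hospitalisation risk of 5% to 15% gives 5 to 15 admissions.

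**The case against.** The strongest reply is that much is already in place. RAMP participants who attend sessions are checked there even if they skip surveys, and section 6.2.2 has adverse events asked about at study visits as well as at data collection. Staff follow up missed sessions. Survey non-responders are emailed, mailed, phoned and texted, can answer by phone, and are traced through the Joint Legacy Viewer (section 5.5). A participant who misses 3 months but answers at 6 is asked about the time since the last survey. Death is a named withdrawal reason (section 5.6.3), reasons are recorded, and the DSMB sees them tabulated. The IRB deemed the risks minimal, and the DSMP was revised on DSMB advice. All of this stands, and it limits the point. It does not remove it, because tracing aims at survey completion and gives no systematic coverage of death or admission.

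A reader might infer more than the documents support:
- **That a fifth of participants have no safety check, or that up to 43% of SAEs will be lost.** The 20% is an upper planning bound that includes partial responders, and the loss shares assume nothing is found by other means.
- **That deaths will be filed as missing surveys.** This can happen only where tracing fails to uncover the death.
- **That the EHR is never used for safety.** Chart review at screening serves that purpose; the gap is after enrolment.
- **That the plan contradicts itself.** DSMP 6.2 promises only to record events that reach the team, and the separate reporting row for deaths covers those at least possibly related to the research.

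**Conclusion.** The concern holds in a limited form. It is a weakness of design that is inexpensive to mend, and the documents do not contradict each other on it. Post-enrolment ascertainment has no source independent of participant or staff contact. The gap falls on Usual Care participants who miss surveys throughout, on RAMP participants who miss them after sessions end, and on everyone in the final 30 days. The unequal intensity between arms (11 scheduled occasions against 2) bears most directly on the by-group SAE tables and would remain with full survey response.

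The textual finding is firm. Its size is not: at most 100 of 500 participants have incomplete survey coverage, or about 70 at the earlier trial's follow-up. The number of events actually missed cannot be derived from the documents. The capture shares and event counts rest on an assumed relative risk and assumed event rates. Sample size, power and alpha are unaffected.

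**What to change.** Add a fourth source to DSMP section 6: a scheduled query of the linked VHA EHR for death and inpatient admission, run identically for every randomised participant in both arms. Run it before each semi-annual DSMB report and once at the end of the 30-day window. State the date on which that window closes for someone who never returns the final survey. Exclude participants who have asked that their data not be used (section 5.6).

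In the closed report, show EHR-detected and survey-detected SAEs separately by group, so that one set of counts has a common basis in both arms. Check vital status before classifying anyone as lost to follow-up.

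The cost is a DSMP and protocol amendment and a recurring query by the existing data group. Further data-access authorisation may be needed, since section 7.0 has extracts requested as needed through a tracked process. There will be additional events to adjudicate. Admissions outside the VHA will still depend on self-report, and the report should say so.

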To facilitate recruitment of patients who may not have reliable access to a device and/or broadband internet, the recruitment materials will: 1) Include instruction on the option to use a smartphone to access the website, and 2) encourage participants who do not have access to a device with internet or a smartphone to call the study phone number to discuss other means to connect and participate. Patients who call the study line will have this information reviewed verbally by project staff, who will then discuss options with interested patients. We will assess the utility of these approaches in the UG3/Phase 1 pilot study, via qualitative feedback. To facilitate recruitment and retention of racial/ethnic minority and female patients we will solicit and incorporate feedback on our recruitment materials and recruitment/retention strategies from patient and community partners/advisors from those groups. If goals for racial/ethnic minority and female patients are not being met, we will adjust our sampling strategy (e.g., increase the proportion of patients from under-supported groups in the subsequent recruitment waves) to achieve our goals, a strategy that was used successfully in the LAMP trial.

RANDOMIZATION

Allocation concealment methods were designed to maximize internal validity within the constraints of the study design.^{35,36} The computer-generated randomization list is concealed from the research team conducting eligibility assessments and participant enrollment using a centralized electronic randomization system.

BLINDING

For the UG3, blinding is not possible because of the design (single group). All enrolled participants are assigned to the RAMP intervention.

For the UH3, upcoming treatment assignments will be concealed from study staff involved in screening and enrollment until after randomization through the electronic study application. All investigators will be blinded to the primary and secondary outcomes data until the study database is locked for analysis. Investigators are authorized to be unblinded when needed for safety-related processes (e.g., adjudication of serious adverse events, decisions to withdraw participants from the intervention following adverse events).

RETENTION

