6.2.2 Adverse Event Monitoring

We will monitor and report adverse events and unanticipated problems involving risk to subjects or others (UPIRTSO) to our local IRB, DSMB, and the funding agency as required. Active and passive surveillance methods will be used to monitor for adverse events. We will ask about potential adverse events at all study visits and data collection events. Participants will also be asked to notify study personnel (outside of scheduled sessions and reporting) about serious adverse events that occur. Trained project staff will be responsible for documenting adverse events and notifying the principal investigators. The MPIs will have final determination regarding the classification and reporting of adverse events to applicable regulatory bodies (e.g., IRB, DSMB, funding agency). The MPIs will report serious adverse events and unanticipated problems to the appropriate regulatory bodies within 5 business days or other required amount of time.

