Informed consent: The Project Director (and other team members, as required) will follow IRB guidelines when preparing for compliance audits of the study overall and informed consent documentation. The Minneapolis VA IRB reviews 100% of documentation of verbal informed consent and HIPAA authorization forms for completion and accuracy. Triennially the Minneapolis VA IRB reviews whether all study materials are properly and securely stored, IRB correspondence and approvals are up-to-date, and personnel training is current.

Outcome data collection: The primary method of data collection for participant self-reported outcomes will be direct electronic entry through a survey interface with Qualtrics FedRAMP. Logic rules specifying the type and range of acceptable responses will be programmed into Qualtrics FedRAMP. Participants will receive an error message

if they enter an invalid response. The MPIs will review reports on data capture and quality on a monthly basis. Missing data reporting and other customized reports will be developed in order to facilitate efficient workflow and high-quality data capture. Data collection instrument specific follow-up rates will be tabulated and reviewed during meetings between the MPIs and project staff. Additional training will be provided as needed based on the findings.

Intervention Fidelity: Consistent delivery of the study intervention will be monitored throughout the intervention phase of the study. Facilitators will use standardized checklists at each session to document the delivery of session activities. In addition, a total of 15% of intervention sessions will be assessed by an MPI (or designee) to ensure session activities are delivered as intended (goal: 90% of all activities are delivered). The MPIs will meet at least two times per month to review barriers to session activities and implement additional training as needed.

Protocol Deviations: Protocol deviations will be documented by the Project Director and designees. The MPIs will review protocol deviations at least two times per month, and will implement corrective actions, as appropriate, or when the quantity or nature of deviations are deemed to be at a level of concern. Protocol deviations will be reported to NINR and the DSMB in the semi-annual reports.

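### Investigators close to RAMP may know the arm when they confirm SAE severity, and the DSMB tables show no count from before adjudication

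*Combined protocol and SAP*

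**What the plan says.** Appendix A (DSMP), section 6: "Events identified as serious adverse events or unanticipated problems will be adjudicated by the MPIs and Co-Is for: confirmation of severity, relatedness and expectedness". Protocol section 6.2.2 adds: "The MPIs will have final determination regarding the classification and reporting of adverse events".

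DSMP section 6.2.1 uses one four-grade severity scale. Serious is the top grade, defined by death, a life-threatening condition, hospitalization or disability.

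On masking, protocol section 5.2.2 (Blinding) first sets a general rule: "All investigators will be blinded to the primary and secondary outcomes data until the study database is locked for analysis". It then makes an exception: "Investigators are authorized to be unblinded when needed for safety-related processes (e.g., adjudication of serious adverse events". Decisions to withdraw a participant from the intervention are its second example. Neither section describes a masked step or says which of the three judgements needs the arm.

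On who these investigators are, DSMP section 5.2.1, Table 1 (Intervention row) says: "Facilitators will be trained and supervised by the clinical psychologist MPI, chiropractic MPI, and Co-Is with clinical pain management experience". DSMP section 7 (Intervention Fidelity) has an MPI or a designee assess 15% of sessions.

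On use of the result, the protocol's Schedule of Activities (section 2.3, Table 3) places adverse events in the Secondary Outcomes block. DSMP section 7.5 gives the DSMB closed tables by group, with counts and rates of adverse events, SAEs and unanticipated problems.

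**The concern.** Confirming severity decides whether an event stays an SAE. The criteria are mostly factual but leave some discretion: a hospital stay must have resulted from the event, disability includes lasting change in quality of life, and life-threatening turns on potential risk of death. Most of these calls can be made without knowing the arm, yet the permission to unblind covers adjudication as a whole.

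If someone who supervises the programme knows the arm, borderline events could be downgraded more readily in one arm than in the other. The SAE comparison shown to the DSMB would then be distorted, and confirmed counts alone would not reveal it. The same adjudication settles relatedness and expectedness, which fix the reporting timeline. In DSMP Table 3, an unexpected and at least possibly related non-fatal SAE goes to the IRB within 5 business days and to the DSMB and NINR within 7. An expected one waits for continuing review or the annual report.

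**Working it through.** **1. The plan's own figure.** The documents give no SAE rate and no power for safety. The only power figure is for BPI interference (protocol section 5.8): 200 per arm, effect size 0.3, correlation 0.7 between two follow-ups, alpha 0.05 (taken as two-sided).
- SD of the two-visit mean: √((1 + 0.7)/2) = 0.922.
- Standardized difference: 0.3/0.922 = 0.325. Standard error: √(2/200) = 0.1.
- Power = Φ(3.25 − 1.96) = 90.2%, matching the stated 90%.
- Attrition: 400/(1 − 0.20) = 500 randomized, so 250 per arm.

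Nothing in this point changes these figures.

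**2. The text, step by step.**
- MPIs and Co-Is confirm severity (DSMP 6), and Serious is a severity grade (DSMP 6.2.1). Confirmation can therefore move an event out of the SAE row.
- Unblinding is allowed for SAE adjudication when needed (protocol 5.2.2), with no split between severity and the other two judgements.
- Two MPIs and the Co-Is with pain management experience supervise facilitators (DSMP 5.2.1, Table 1), so they overlap with the adjudicators.
- The report outline (DSMP 7.5) asks for counts and rates, with no comparison of first-reported against confirmed events.
- The unaltered data are preserved and recoding is documented (DSMP 8.4.1). The count before adjudication could therefore be produced, but no report is planned to show it.

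**3. Illustration of size.** Assumptions: 250 per arm, equal true SAE risk r in both arms, and a share q of RAMP SAEs not confirmed while every Usual Care SAE is. Spurious difference = r × q; events lost = 250 × r × q.

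| r | q | Usual Care events | RAMP events confirmed | Difference | Risk ratio |
|---|---|---|---|---|---|
| 3% | 5% | 7.5 | 7.1 | 0.15 points | 0.95 |
| 10% | 10% | 25 | 22.5 | 1.0 point | 0.90 |
| 10% | 20% | 25 | 20 | 2.0 points | 0.80 |
| 15% | 20% | 37.5 | 30 | 3.0 points | 0.80 |

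The range is 0.15 to 3.0 percentage points, or about 0.4 to 7.5 events. If the true counts were 30 against 25 (ratio 1.20), losing one RAMP event in five would show 24 against 25 (0.96); losing one in ten would show 27 against 25 (1.08).

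**4. Against sampling error.** For 20 against 25 of 250, SE(log RR) = √(1/20 + 1/25 − 2/250) = 0.286, so the ratio of 0.80 has a 95% interval of about 0.46 to 1.40. For 30 against 25, SE = √(1/30 + 1/25 − 2/250) = 0.256, and the ratio of 1.20 has an interval of about 0.73 to 1.98. Neither would be a clear statistical signal.

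**The case against.** A reader might infer more than the documents support, and the strongest objections are to those readings.

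- **That every adjudication is unmasked.** The text permits unblinding only when needed, and nowhere says the three judgements are made together.
- **That adjudicators and RAMP supervisors are the same people.** Protocol section 8.0 refers to three MPIs; two are named as supervisors, with only some Co-Is, and a designee may check fidelity. The overlap is substantial but not shown to be complete.
- **That the adverse-event secondary outcome rests on this judgement.** The row covers adverse events generally. Protocol section 3.3.3 collects a participant checklist with the participant's own relatedness rating, plus questions on hospital stay, disability and life-threatening events. Adjudication covers only events identified as SAEs or unanticipated problems.
- **That the count before adjudication is lost.** DSMP section 8.4.1 contradicts this, and a downgraded SAE should still appear among adverse events.
- **That the bias favours RAMP.** The illustration builds that direction in. Staff observe events during RAMP sessions, while Usual Care participants only complete surveys, so uneven ascertainment could push the other way.

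Three further objections stand as limits on the remedy. One life-threatening criterion refers to the study interventions, so severity is not wholly separable from arm. The reporting timelines turn on relatedness and expectedness, which would still be judged with the arm available. And adjudicators may already know the arm, because session events are notified to the MPIs and participants may contact an MPI directly.

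The objections do not remove two gaps: the permission to unblind has no stated boundary, and no planned table shows the effect of adjudication.

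**Conclusion.** The point holds in a limited form. The plan allows, but does not require, SAE severity to be confirmed with knowledge of arm by investigators several of whom supervise RAMP delivery. No planned DSMB table would show whether confirmation had treated the arms differently. What is exposed is the SAE and unanticipated-problem classification, and nothing wider.

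The size and net direction cannot be established from the documents. The 0.15 to 3.0 percentage points are an illustration resting on assumed SAE risks, assumed downgrade rates and one-sided downgrading. They show that a few reclassified events could shift a sparse table, not that this will happen. The DSMB's review by arm is a real safeguard, and the data needed to strengthen it are already collected. This is an inexpensive improvement to the safety reporting, not a flaw that threatens the trial's main conclusion.

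**What to change.** 1. **DSMP section 6.** State that seriousness and severity are confirmed and recorded first, from a narrative with arm, session and coach references removed where feasible. The Project Director or designee, who already records events, could prepare it.
2. **Protocol section 5.2.2 (Blinding).** Limit unblinding for adjudication to the later relatedness and expectedness step, and to any seriousness criterion that refers to the intervention.
3. **DSMP section 7.5 and the final safety table.** Show SAEs by arm as first reported and as confirmed. In the first-reported count, show the three follow-up survey items (overnight hospital stay, severe or permanent disability, life-threatening event), asked identically in both arms, separately from staff-observed events.

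Existing reporting timelines stay unchanged, and the masked step must not delay a report.

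The cost is a few sentences of amendment, with the IRB approval that any amendment requires, plus some redaction per event and extra tabulation. The documents give no workload figure, so calling this small is a judgement. No extra assessor, visit or data item is needed. Masking will be incomplete for events in a RAMP session or reported directly to an MPI. The side-by-side counts matter most there, because they would show differential reclassification even where masking fails.
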